#### 10.2 Proposed Analysis

All statistical analyses will be governed by a comprehensive Statistical Analysis Plan, which will be authored by the study statistician and approved by the Trial Steering Committee and the Data Monitoring Committee before the main study outcome data are examined. All analyses will be carried out using Stata. In accordance with CONSORT guidelines, we will report all participant flow. Descriptive statistics of recruitment, drop-out and completeness of interventions will be provided.

Effectiveness Analysis: The main effectiveness analysis will be via intention-to-treat including all participants, with no planned interim analysis for early termination for either overwhelming evidence of effectiveness or abandoning for futility. Baseline characteristics will be presented by randomised group without formal statistical tests. We will test the primary hypothesis for between-group change in the primary outcome for each of the two pre-specified comparisons (CBA + usual care vs usual care alone and PEP + usual care vs usual care alone) using repeated measures mixed model, with subject as a random effect, and a suitably specified covariance structure (e.g. Autoregressive [1] (AR[1]), rheumatology healthcare professional as a random effect (to adjust for any clustering by rheumatology healthcare professional), with baseline outcome measure, and any other strongly predictive baseline measures, including the minimisation factors of presence/absence of depression and centre, and diagnosis. Treatment and its interaction with time will be fitted as fixed effects, and we apply standard regression diagnostics. The analysis will use statistical techniques for handling missing outcome data using multiple imputation under a missing at random (MAR) assumption. The secondary outcomes will be analysed using an analogous method. The main estimate of treatment effect will focus on the 56 weeks after baseline.

*Mediation analysis:* We will use modern causal inference methods to investigate the set of mediator measures. If the effectiveness analysis shows significant between group differences in the mediators then we will use parametric regression models to test for effect of mediator on outcome, and the residual direct effect of treatment on outcome. Since all the measures are continuous, the indirect effects are calculated by multiplying relevant pathways and bootstrapping is used to produce valid standard errors for the indirect effects. All analyses will adjust for baseline measures of the mediators, outcome and putative measured confounders, and be tested for moderation by diagnosis. Mediation analyses are potentially biased by measurement error in mediators and hidden confounding between mediators and outcomes; we will build on our previous methodological and applied work in this context to include repeated measurement of mediators and outcomes to account for classical measurement error and baseline confounding. We will investigate the sensitivity of the estimates to these problems and that of unmeasured confounding using instrumental variable (IV) methods with baseline covariate by randomisation interactions as potential instruments.

*Moderation analysis:* We will examine differential treatment effects using the set of moderator measures by extending the intention to treat analysis models to include an interaction term between treatment and each of the moderators separately. We will use bias correction/cross-validation methods to identify robust evidence for individual moderation and for a moderation index, both on the overall effect and also along the steps of the mediation pathway.

# 10.3 Missing Data

Every effort will be made to ensure data collection is complete. However, we will use statistical techniques for handling missing outcome data. Multiple imputation under a MAR assumption will be used in the first instance, with other methods employed if the MAR assumption is not satisfied.

# 11 TRIAL MANAGEMENT AND OVERSIGHT ARRANGEMENTS

# 11.1 Trial Management Group

The study will be co-ordinated by a Trial Management Group, consisting of the grant holder (Cl), a rheumatology consultant (Co-Cl), additional members of the Epidemiology group, a study co-ordinator and a representative from CHaRT. The members of the Trial Management Group and their responsibilities are summarised in the delegation log in the TMF. In addition, the names and responsibilities of all co-investigators are also summarised in the delegation log in the TMF.

# 11.2 Study Management

A Study co-ordinator (or designated deputy) will be responsible for the overall day-to-day management of the study and will be accountable to the CI, the Co-CI and investigators. He/she will ensure that personal and confidential information is restricted to those entitled to know it, will assist in the compliance with research and clinical governance guidelines, data protection and ethical requirements.

A Study co-ordinator (or designated deputy) will establish and maintain procedures to ensure adherence to study protocols, SOPs and administrative requirements. He/she will be responsible for training and monitoring the study staff at the local sites involved in

recruitment and assessment of the participants. He/she will assist in monitoring the study progress to ensure compliance with and adherence to the project plan and identify, evaluate and rectify problems. He/she will be responsible for checking the outcome documents for completeness, plausibility and consistency. However, this remains the overall responsibility of the CI. Any queries will be resolved by the CI or delegated member of the study team.

# **11.3 Trial Steering Committee**

A Trial Steering Committee (TSC) has been established to oversee the conduct and progress of the study. The TSC comprises an independent chair who has expertise in trials and other members, both independent and study investigators, with background relevant to IRD or type of interventions including user representatives, who have lived experience of IRD related fatigue, and a clinician working with people with IRD. The members of the TSC are documented in the TMF at the study centre Aberdeen.

# **11.4 Data Monitoring Committee**

An Independent Data Monitoring Committee (IDMC) has been established to oversee study progress. The members of the IDMC are summarised in the TMF at the study centre Aberdeen.

## **12 INSPECTION OF RECORDS**

Investigators and institutions involved in the study permit study related monitoring and audits on behalf of the sponsor, NHS R&D and REC. In the event of an audit or monitoring, the Investigator agrees to allow the representatives of the sponsor direct access to all study records and source documentation.

#### 13 GOOD CLINICAL PRACTICE

#### **13.1 Ethical Conduct of the Study**

The study will be conducted in accordance with the principles of good clinical practice (GCP). In addition to Sponsorship approval, a favorable ethical opinion will be obtained from the appropriate REC and appropriate NHS R&D approval(s) will be obtained prior to commencement of the study. A collaboration agreement and site agreements will be signed between The University Court Of The University Of Aberdeen and the included parties and study sites, respectively.

#### 13.1.1 Confidentiality

All laboratory specimens, evaluation forms, reports, and other records will be identified using unique participant ID numbers to maintain participant confidentiality. All records will be kept in a secure storage area with limited access to study staff only. Clinical information will not be released without the written permission of the participant, except as necessary for monitoring and auditing by the Sponsor or its designee. The investigators and study staff involved with this study will not disclose or use for any purpose other than performance of the study, any data, record, or other unpublished, confidential information disclosed to those individuals for the purpose of the study.

## 13.1.2 Data Protection

All Investigators and study staff involved with this study will comply with the requirements of the Data Protection Act 2018 with regard to the collection, storage, processing and disclosure of personal information and will uphold the Act's core principles. The investigators and study staff will also adhere, if appropriate, to the current version of the NHS Scotland Code of Practice on Protecting Patient Confidentiality. Access to collated participant data will be restricted to the CI and appropriate study staff as needed.

Computers used to collate the data will have limited access measures via user names and passwords, and such documents will be password protected and stored on secure University or NHS servers. Published results will not contain any personal data that could allow identification of individual participants.

#### 13.1.3 Insurance and Indemnity

Where the study involves University of Aberdeen staff undertaking clinical research on NHS patients, such staff will hold honorary contracts with Grampian Health Board, which means they will have cover under Grampian's membership of the CNORIS scheme.

# 14 STUDY CONDUCT RESPONSIBILITIES

#### 14.1 Protocol Amendments, Deviations and Breaches

The CI will seek approval for any amendments to the Protocol or other study documents from the Sponsor, REC and NHS R&D Office(s). Amendments to the protocol or other study documents will not be implemented without these approvals. It is the responsibility of the sponsor to designate amendments as substantial or non-substantial.

In the event that a CI needs to deviate from the protocol, the nature of and reasons for the deviation will be recorded in the CRF, documented and submitted to the Sponsor. If this necessitates a subsequent protocol amendment, this will be submitted to the Sponsor for approval and then to the appropriate REC and lead NHS R&D Office for review and approval.

In the event that a serious breach of GCP is suspected, this will be reported to the Sponsor immediately using the "Breach Report Form".

# 14.2 Study Record Retention

All study documentation (hard copy and electronic) will be kept for a minimum of 5 years from the protocol defined end of study point in the University of Aberdeen archive. When the minimum retention period has elapsed, study documentation will not be destroyed without permission from the sponsor.

# 14.3 End of Study

The end of study is defined as last data collection of either the qualitative evaluation study phase or during the last follow-up visit at 56 weeks from the last participant after CBA/PEP intervention or usual care start date – whichever comes last.

## 15 REPORTING, PUBLICATIONS AND NOTIFICATION OF RESULTS

#### **15.1 Authorship Policy**

Ownership of the data arising from this study resides with the University of Aberdeen. On completion of the study, the study data will be analysed and tabulated, and a clinical study report will be prepared in accordance with ICH authorship guidelines.

#### 15.2 Publication

The clinical study report will be used for publication and presentation at scientific meetings. Investigators have the right to publish orally or in writing the results of the study.

#### 15.3 Peer Review

The initial study proposal was peer reviewed extensively within the system of the University of Aberdeen, as well as experts in the field before the grant application was submitted to Arthritis Research UK. Furthermore, representatives of the National Rheumatoid Arthritis Society, the National Ankylosing Spondylitis Society and Lupus UK significantly influenced the study design. In addition, the proposal underwent review from the funding agency (Arthritis Research UK). Any documents created as part of this project will undergo peer review internally within the research team, and representatives of the National Rheumatoid Arthritis Society, the National Ankylosing Spondylitis Society or Lupus UK.

#### Background

Recruiting and retaining participants for randomised trials can be extremely difficult. It is likely that less than 50% of trials meet their recruitment target, or meet their target without extending the length of the trial [1-3]. Moreover, poor recruitment can lead to an underpowered study, which may report clinically relevant effects to be statistically non-significant. A non-significant finding increases the risk that an effective intervention will be abandoned before its true value is established, or that there will be a delay in demonstrating this value while more studies or meta-analyses are done. Moreover, if non-responses to the study invitation differ between the patients with diagnosis of RA, SLE and AxSpA, a systematic bias may be introduced that may undermine confidence in the results of the trial. Finally, poor recruitment and subsequently retention can lead to a trial being extended, increasing costs.

Trialists recognise the challenge and use many interventions to improve recruitment and retention but it is generally difficult to predict their effect. The Cochrane systematic review of strategies to improve recruitment [4] and the Cochrane review of strategies it improve retention [5] both found only a handful of interventions with high quality evidence of benefit. Given how central recruitment and retention are to all trials, it is crucial that more rigorous evaluations of recruitment and retention interventions are done.

#### Rationale for SWAT

One way of doing this is to do a Study Within a Trial (SWAT) [6]. A SWAT provides a protocol for the evaluation of an intervention to improve some part of the trial process, such as recruitment or retention. This evaluation is then embedded within a host trial, such as LIFT. Several teams can follow the same SWAT protocol, meaning the results can be combined in a meta-analysis. This coordinated and collaborative approach means trialists will have faster access to high-quality evidence to inform their trial design, conduct, analysis and reporting decisions.

The SWAT 24 which describes the use of a theory-based cover letter was initially developed to increase response rates of questionnaires sent during follow-up to collect outcome data direct from participants. A low response rate to these questionnaires puts the validity and generalisability of the trial results in jeopardy. Since returning the questionnaire is a behaviour, this opens up the possibility of designing a behaviour change intervention to influence the willingness of participants to do that behaviour. We propose to use SWAT 24 in LIFT to improve response rates to the pre-study invitation letter used to make initial contact with potential participants identified as described in the main protocol (see 5.2.1) to explore interest and eligibility. The SWAT 24 study is part of the Trial Forge initiative to improve trial efficiency [7].

#### **Objective for SWAT 24**

To assess the effects of a theory-based cover letter on response rate to a pre-study invite to explore interest and eligibility

Lessening the Impact of Fatigue in IRD

#### Outcome

Primary outcome:

Response rate

Secondary outcomes: Response time Consent rate Study retention Intervention adherence

#### Intervention

The Theoretical Domains Framework (TDF) is a tool for identifying theoretical targets for behaviour change interventions [8]. The TDF and behaviour change techniques were used by the IQuaD trial team [9] to produce a template that trial teams can use to structure a theory-informed cover letter.

#### Comparator

A standard cover letter

#### Method for allocating to intervention or comparator

Participating study centres will be randomly allocated to send the standard letter or the theory-informed letter.

#### Analysis plan

The primary analysis is the difference in primary and secondary outcomes between those receiving the theory-based cover letter and those receiving the standard cover letter.

# Appendix 2: Delineating the neural mediators of inflammatory rheumatic disease (An optional LIFT sub-study)

# Background

One of the objectives of the LIFT trial is to understand the mediators of treatment effect which will enable optimising of interventions and inferences to be made regarding the mechanisms of fatigue. We are collecting putative patient reported, clinical and physical activity profile mediator data. In addition we would like to provide the option for participants to provide their neuroimaging data by undertaking additional MRI scans of their brain.Neuroimaging has provided consistent mechanistic insights into fatigue, reinforcing our epidemiological investigations of RA related fatigue which have identified strong associations with central factors such as mental health and cognitive dysfunctions but not peripheral measures of inflammation. We were the first to test these methods in a fatigued chronic inflammatory disease cohort. We identified multiple neural correlates of fatigue in patients with vasculitis using different structural and functional magnetic resonance imaging (MRI) modes  and we have since observed similar fatigue specific findings in RA.

Our original studies were small (n=12) and cross-sectional but did implicate a potential role for a striato-thalamo-frontal network. Among fatigued vasculitis patients, we observed an apparent overuse of the cingulum and fornix white matter tracts, as identified by Diffusion Tensor Imaging (DTI), which coincided with the high functional activity within some of their source and destination grey matter structures, specifically the thalamus, medial globus pallidus, medial frontal and cingulate gyri and paracentral lobule.

Our most recent pilot was larger and although uncontrolled included a repeat multi-modal scan at 6 months that enabled the longitudinal evaluation of fatigue in the context of standard care (which did not include fatigue specific therapy). Of those n=54 completing follow up, n=22 reported modest, albeit clinically relevant, improvements in their fatigue. Interestingly, widespread reductions in cortical grey matter volumes were measured, using voxel-based morphometry (VBM), among the non-improvers at follow-up however no such volume changes were observed among improvers. In contrast, sub-cortical grey matter volumes exhibited large significant increases in non-improvers. The sub-cortical grey matter volumes of improvers also increased, although the changes were small in comparison.

In terms of white matter integrity, as measured by DTI, widespread abnormalities were observed among improvers. Within this group, significantly reduced fractional anisotropy (FA) was measured at follow-up compared to baseline in major white matter tracts. Strikingly, no significant longitudinal FA changes were measured within the non-improvers group. Similarly, improvers- and not non-improvers- evidenced widespread imbalances in functional connectivity imbalance over time.

Overall, these data strongly associate central neural pathways in RA related fatigue. Although the different MRI metrics provide complementary evidence which implicate frontal networks, a targeted approach (e.g. with non-invasive neuromodulation devices) will demand much greater knowledge of the precise culprit frontal regions, moreover several non-frontal regions seem also to be relevant. Until now, no studies have been adequately designed to pin-point those brain regions which mediate changes in fatigue (and so demonstrate causal potential).

The problem with our existing studies is that they were either cross-sectional, or longitudinally followed individuals who had spontaneous changes in their fatigue (thus the changes in fatigue from one time point to the next were modest). We propose that the best way to identify which of these brain regions are most important in mediating fatigue is to perform controlled longitudinal imaging studies in individuals prior to and then following an intervention that reliably improves fatigue in most individuals.

This Lessening the Impact of Fatigue Trial (LIFT) sub-study provides a timely opportunity to address this research void.

#### Sub-study objective

• Which functional and structural brain mediators best explain fatigue improvement and are they potentially trans-cranially accessible?

#### Study design

An optional nested mechanistic observational sub-study within the Lessening the Impact of Fatigue Trial (LIFT).

#### Participants

All consenting LIFT participants will be invited to participate in this optional sub-study which involves an additional MRI brain scan prior to and 26 weeks after their first treatment session (if CBA or PEP) or within 8 weeks of randomisation and 6 months thereafter if usual care. The only additional exclusion criteria is any contra-indications to MRI scanning (e.g. pacemaker).

#### Participant selection

At the baseline visit, all participants will be provided an information sheet on this substudy. The research team will then contact the participants a few days later to establish interest and the absence of MRI contraindications. If suitable and interested, the participant will be offered an appointment to attend their nearest participating MRI research facility (Edinburgh, Aberdeen or Glasgow) within a month. A research team member, recorded in the Delegation Log and with GCP training, will be responsible for taking additional full written informed consent (specific to this sub-study) on attendance at the imaging centre prior to the MRI assessment and then conduct a final MRI safety screen.

#### Participant withdrawal

All participants will be free to withdraw at any time from the MRI sub-study, without giving reasons and without prejudicing further treatment or their participation in the LIFT trial.

#### MRI assessment

Prior to entering the scanner, subjects will have the opportunity to practice a cognitive task required for the standard fMRI aspect of analysis. As with our previous work, the validated PASAT will be employed to transiently fatigue the subject. The task is a measure of cognitive function; specifically auditory processing, calculation, working memory and attention. Participants will be asked to listen to a series of numbers ranging from 1 to 9. They are required to sum consecutive numbers (i.e. the first to the second, the second to the third etc.) and to record, via a button press, every occasion two consecutive numbers sum to the number 10. Concurrently, they will be asked to focus on a computer screen displaying three boxes containing random, rapidly changing numbers. This visual stimulus is intended to distract the participants from the auditory task and hence increase difficulty. They will be instructed not to process the visual numbers in any way.

Participants will then be asked to lie supine in the 3T Phillips Achieva X-series MRI scanner in Aberdeen or the equivalent scanner in Edinburgh. The multi-modal MR will consist of structural and functional sequences:

*Structural-* We will collect images to allow volumetric analysis. We will also acquire images to allow determination of white matter hyperintensity lesion load and measures of white matter structural integrity (e.g. DTI).

*Functional Imaging*- Images sensitive to BOLD contrast will be acquired during rest to investigate metrics such as intrinsic network connectivity as well as during the PASAT task (3x3minute periods interspersed by 30s rest periods).

In total these can will take approximately 45 minutes to conduct and will be repeated at approx. 6 months (when we predict to observe the greatest effect from the interventions).

#### Analysis

Following pre-processing of the MRI data the following analysis will be undertaken which will integrate data which will have been collected as part of the parent trial:

Longitudinal comparisons (paired t-tests as implemented by SPSS for ROI based variables and Freesurfer for voxel based variables) of structural and functional change indices in relation to subjects' change in fatigue will be performed. Putative confounders will be individually introduced as co-variates of interest. The individual analyses will focus upon those regions of interest previously identified by our studies, but since we recognise that these are not comprehensive we will also conduct agnostic (data-driven) whole brain analyses. All analyses will be adjusted for multiple testing.

Having identified and validated key neural areas, group differences in mediators of treatment effects on outcomes will be assessed via mediation analysis methods in order to tackle the secondary objective. These involve causal inference methods, such as structural equation modelling, to account for measurement error in the imaging data, and repeated measures to allow for the inclusion of all available data. Those resultant neural mediators which are common to both interventions and accessible to non-invasive neuromodulation will serve as our future therapeutic targets.

Finally we will be using whole brain statistical pattern recognition techniques on the neuroimaging data and mediation effects identified in answer to the previous objective. In the Pattern Recognition for Neuroimaging Toolbox (PRoNTo) brain scans are treated as spatial patterns and statistical learning models are used to identify statistical properties of the data that can be used to discriminate between, or classify, experimental groups of subjects.

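### MRI sub-study: the named paired t-tests cannot test whether brain change relates to change in fatigue, and validation of regions found only by the whole-brain search is not described

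*Protocol*

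**What the plan says.** Protocol Appendix 2, Analysis, describes longitudinal comparisons "of structural and functional change indices in relation to subjects' change in fatigue will be performed". The tool it names is "paired t-tests as implemented by SPSS for ROI based variables", with Freesurfer doing the same for voxel data. The next sentence adds: "Putative confounders will be individually introduced as co-variates of interest".

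Regions come from two sources. The main one is prior work: "The individual analyses will focus upon those regions of interest previously identified by our studies". Because the team regards that list as incomplete, "we will also conduct agnostic (data-driven) whole brain analyses". The section says that all analyses are adjusted for multiple testing, but gives neither method nor family.

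The plan then moves to causal mediation methods, such as structural equation modelling, with the words "Having identified and validated key neural areas". How an area is validated is not stated. Mediators shared by both interventions and reachable by non-invasive neuromodulation are to become therapeutic targets.

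The sample size section of the appendix gives a target of 120 over the three arms, with no significance level, power or effect size. The SAP limits itself in its Introduction to the main trial, so it does not replace or complete this analysis.

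**The concern.** The question and the test do not match. Whether a region changed on average between two scans is one question; whether people whose region changed more also had more change in fatigue is another. A region can drift in everyone, for example through ageing, disease or scanner effects, and say nothing about fatigue. A region can also track fatigue closely while its mean change is zero, because some participants rise and others fall. The named test flags the first kind and misses the second. The covariate sentence adds a practical difficulty, since a paired t-test has no place for covariates and the analysis cannot be run as written.

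The second issue is narrower. If a region enters the mediation step only because a whole-brain search found it linked to fatigue change in these participants, the mediator-to-outcome path in the same participants has already been selected to look strong.

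At stake is the choice of brain regions for later neuromodulation work.

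**Working it through.** **Inputs.** n = 120 (Appendix 2, Sample size). Assumed, because the documents give no values: mean brain change of 0, 0.2 or 0.3 SD of the change score; true correlation between brain change and fatigue change of 0 or 0.4; complete pairs; two-sided 5% level without adjustment. The 120 has no stated basis, so there is no figure of the plan's own to reproduce.

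**Step 1: what the paired t-test responds to.**

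t = mean(D) / (SD(D)/√n), where D is scan 2 minus scan 1. Fatigue change does not appear. With a true mean change of δ SD, t is non-central with λ = δ√n and n − 1 = 119 degrees of freedom; the critical value is 1.980.

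- δ = 0: rejection 5%.
- δ = 0.2: λ = 0.2 × 10.954 = 2.19; rejection 58%.
- δ = 0.3: λ = 0.3 × 10.954 = 3.29; rejection 90%.

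These rates are the same whatever the correlation with fatigue change. So with a true correlation of 0.4 and δ = 0, the paired t-test still rejects in only 5%.

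**Step 2: what a test of association responds to.**

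t = r√((n − 2)/(1 − r²)). By Fisher's z, with correlation 0.4: atanh(0.4) × √117 = 0.4236 × 10.817 = 4.58; power = Φ(4.58 − 1.96) = Φ(2.62), over 99%. With correlation 0 it rejects in 5% for any mean change.

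| Truth | Paired t-test | Association test |
|---|---|---|
| Mean change 0.2 SD, correlation 0 | 58% | 5% |
| Mean change 0.3 SD, correlation 0 | 90% | 5% |
| Mean change 0, correlation 0.4 | 5% | >99% |

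A simulation of 4,000 studies per row agrees (58%, 91% and 5% for the paired t-test; 5%, 5% and >99% for association).

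**Step 3: sensitivity.** The plan promises multiplicity adjustment. At 0.05/10 = 0.005 (10 regions, assumed), the paired t-test rejects in 26% and 67% for 0.2 and 0.3 SD with no fatigue link, and the association test has power Φ(4.58 − 2.81) = 96% at correlation 0.4. If 20% had no second scan (the main trial's dropout rate, assumed to apply here), 120 × 0.8 = 96 pairs give 49% and 83% at the 5% level. Adjustment and attrition change the rates but not the question being tested.

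**Step 4: how a region reaches the mediation step.** I simulated 1,000 studies per setting: 40 per arm, complete data, independent regions, a treatment effect of 0.5 SD on both brain change and fatigue change, and no true mediator-to-outcome path. The table shows false positives for that path, adjusted for arm, at a nominal 5%.

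| How the region is chosen | 10 regions | 100 | 1,000 |
|---|---|---|---|
| Fixed in advance | 6% | 4% | 5% |
| Largest pooled paired t | 4% | 5% | 6% |
| Strongest link with fatigue change, same data | 30% | 87% | 100% |
| Any region passing a Bonferroni search on that link, same data | 11% | 16% | 20% |
| Chosen on one half, tested on the other | 3% | 4% | 6% |

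Circularity therefore arises only when regions are selected on their link with fatigue change and tested in the same people. The 30% to 100% row is an extreme, since it always takes the best region forward without adjustment. Correlated regions would reduce the effective number of tests.

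**The case against.** The wording may simply be loose. A sentence that mentions change in fatigue and covariates probably has some form of regression in mind. That is plausible, but the only method named is one that can do neither, and no other document corrects it.

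Three stronger readings are tempting, and the documents do not support them.

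- *That all mediation is circular.* The stated focus is on regions from the team's earlier studies. For those, selection is independent of these data and the false-positive rate is nominal. Multiplicity adjustment and validation are both mentioned; what is missing is how they are done. Nor can one argue both that the first step ignores fatigue and that it selects on fatigue: selection by a literal pooled paired t-test is not circular for the mediator-to-outcome path.
- *That the plan will contrast significance in improvers with non-significance in non-improvers.* The Background section reports pilot results in that style, for example "no significant longitudinal FA changes were measured within the non-improvers group", but it does not name the pilot's test, and the Analysis section defines no improver split. If the pilot proportion were applied (22/54 × 120 ≈ 49 against 71) with equal true change of 0.2 to 0.3 SD in both groups, one group alone would be significant in 45% to 51% of studies at an unadjusted 5% level. This falls to 18% to 42% at 0.005, and is 9.5% at the 5% level when neither group changes. Those figures describe an analysis that the plan does not state.
- *That the mediation method is itself unsound.* Causal mediation methods that allow for measurement error and use repeated measures are named, and I found no fault in them. The open question is only how regions enter.

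**Conclusion.** The main point holds: the named test does not answer the stated question and cannot take the stated covariates. At n = 120 it would flag a region unrelated to fatigue in about 58% or 90% of studies if that region changed by 0.2 or 0.3 SD on average, and would find a region with a true correlation of 0.4 and no mean change in about 5%. These rates rest on assumed mean changes and correlation, complete pairs and an unadjusted 5% level; the mismatch itself rests on none of them.

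The secondary point holds conditionally. For regions found only by the whole-brain search, no hold-out sample, cross-validation or external sample is described. If those regions are chosen on their link with fatigue change, mediation in the same participants is circular. It does not apply to the regions taken from earlier studies.

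This is a minor, inexpensive correction to an optional mechanistic sub-study. It has no bearing on the trial's primary comparison.

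**What to change.** In Protocol Appendix 2, Analysis:

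1. Replace the paired t-tests with a regression or mixed model of follow-up region value on baseline value, continuous change in fatigue, arm and scanner site, with the chosen confounders as covariates. Name the fatigue-change coefficient as the quantity tested. If such a model was intended all along, say so.
2. List the regions carried over from the earlier studies and keep confirmatory mediation to them.
3. For regions found only by the whole-brain search, either select and test them by nested cross-validation or label the results exploratory. Section 10.2 of the Protocol already commits to cross-validation methods for the moderation analysis, so the approach is not new to the trial.

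The cost is a revision of the appendix wording and slightly more analysis work. The scans, visits and sample size stay as they are.
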